This work aims to advance Brain-Computer-Interfaces (BCIs) to provide severely paralyzed persons a natural way of controlling Functional Electrical Stimulation (FES) neuroprostheses for restoring arm and dexterous hand movements. The prospect of using BCI technology for restoring arm and hand movements for reaching and grasping is based on the hypothesis that in a paralyzed human, there is a repeatable and understandable relationship between recordable brain activity and specific aspects of imagined arm movements. Many previous studies have attempted to understand the relationships between brain activity and arm and hand movements in able-bodied monkeys. Little is known about these same relationships in humans, and specifically within the context of trying to control an FES arm and complex hand system. This study will recruit persons who already have BCI and FES systems implanted to take advantage of the possibility of recording high resolution brain activity in human participants. Thus, from this study, we aim to gain a better understanding of how brain signals are related to specific aspects of arm and complex hand movements in humans with paralysis. Additionally, this study will test novel implementations of complex hand movement restoration in Veterans and other persons with chronic hand and arm paralysis.

10. Describe the means of analyzing the data and evaluating the results.

- *State the anticipated methods to be used for analysis and interpretation of the data.*
- *The methods must compliment the design of the study and the nature of the data which is being collected.*

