This nature of this study is exploratory in nature (rather than quantitative) in that we aim to better understand how hand function is encoded in cortical signals, and then use this understanding to develop correlation models for real-time control of an FES neuroprosthesis. We need to tweak several parameters of each model based upon experimental data, and then test the optimized models in actual control experiments. Consequently the number of required subjects is not elucidated by a standard statistical power analysis. The present study does aim to enroll up to four persons with paralysis (C1-C4 SCI, resulting in complete tetraplegia) who already have intracortical brain arrays and FES systems implanted. The study leverages the clinical and recruiting efforts of the separately funded Braingate2 Clinical Trial in Cleveland that recruits persons with C1-C4 SCI to receive BCI and FES systems.

12. The research involves the following procedures conducted by and for what purpose:

PROCEDURE	PERFORMED BY:		PROCEDURE IS:	
	Research Staff	LSCDVAMC Clinical or Support Staff	Standard of Care*	For Research Purposes Only**
Audiotaping / Videotaping Attach VA Form 10-3203 REQUIRED ONLY FOR IN-PATIENT AND OUT-PATIENT SUBJECTS				
Biopsy				
Blood collection				
Chart review – prospective				
Chart review – retrospective				
Review of existing data (ex: registry, Database , etc.)				
X-ray or Ionizing radiation exposure				
Clinical Tests				
Device implantation				
Drug administration				

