EEG, EKG , ECG...etc				
Gene therapy, Genetic analysis				
Pregnancy/Breastfeeding Screening				

PROCEDURE	PERFORMED BY:		PROCEDURE IS:	
	Research Staff	LSCDVAMC Clinical or Support Staff	Standard of Care*	For Research Purposes Only**
Interview, Questionnaire, Diary, Survey (please attach)				
Stool collection, Urine collection, or any Non-surgical Specimen collection				
Surgical procedure or Specimen removal during surgery				
Tissue banking (complete Section 12)				
Use of pre-existing tissues/specimens				
Other (list) : EMG				

- **Standard of care procedures are procedures performed in the course of normal medical care.*
- ***Research Procedures are performed for the purposes of this research alone.*

13. Please describe the research design and all study related procedures.

- *Describe **ALL PROCEDURES ASSOCIATED WITH THIS RESEARCH**. This includes standard of care and research procedures.*
- *For complex studies please include diagrams and tables. Be sure to describe when each procedure will be performed. Be sure to provide information for **each cohort, including normal controls**.*

All study participants will have already had implanted one or two 96-channel microelectrode arrays in the primary motor cortex (M1), as well as stimulating electrodes for restoration of hand and arm function via FES.

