- A spinal cord injury resulting in at least partial arm paralysis
- Participant in BrainGate2 clinical trial, having already received an intracortical array and demonstrated the ability to use the neural signals to control a cursor on a monitor.

Exclusion criteria:

- Profound visual impairments
- Participant in BrainGate2 clinical trial with insufficient recordable neural signals (such that the researchers cannot decode a movement intention command signal)

N/A Chart/data review

31. By role, (PI, Coordinator, etc.) who will assess for eligibility and how will this be accomplished?

Eligibility for the study will be assessed by the principal investigator in consultation with the co-investigator and coordinator.

32. Are any subjects excluded on the basis of race, ethnic group, understanding of English, socioeconomic status, education, gender, or pregnancy?

- *Note: It is appropriate to indicate that you do not anticipate encountering potential subjects who do not speak English based on the population to be studied*

No **Yes - (provide justification):** Non-English speaking subjects will be excluded, since they will need to understand English instructions during the testing sessions.

N/A Chart/data review

33. Will subjects be reimbursed or paid an incentive for participating?

No (skip to item #35) **Yes**

N/A Chart/data review (skip to item #38)

34. How and when will they be paid?

Cash **Check** **Other** -please explain:

Prorated -provide schedule: **Fixed** -provide schedule

35. Will subjects be responsible for any of the costs related to the research?

No Yes- please explain:

36. Will treating physicians, clinicians, or researchers be compensated or paid an incentive for referring or enrolling subjects?

No Yes -please explain:

37. Please describe steps you will take to ensure that subject selection is fair and equitable:

Potential subjects who are already participating in the BrainGate study will be reviewed and discussed by the research team. BrainGate participants are recruited from underrepresented groups in approximately the same proportions as in the population of Northeast Ohio. Since a majority of spinal cord injured individuals are male, we expect to recruit more males than females for this study.

Section 5 – Risks and Benefits

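### Must item 30 be changed because it omits the implanted FES electrodes and sets a broader injury criterion than item 11?

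*Combined protocol and SAP*

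**What the plan says.** The protocol describes its population in several places.

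- **Section 4, item 30** has three inclusion criteria. The first is intact cognition. The second is "A spinal cord injury resulting in at least partial arm paralysis". The third concerns the brain implant: "Participant in BrainGate2 clinical trial, having already received an intracortical array and demonstrated the ability to use the neural signals to control a cursor". There are two exclusions: profound visual impairment and inadequate neural signals.
- **Section 3, item 9** says: "This study will recruit persons who already have BCI and FES systems implanted".
- **Section 3, item 11** words its enrolment goal as follows: "aim to enroll up to four persons with paralysis (C1-C4 SCI, resulting in complete tetraplegia) who already have intracortical brain arrays and FES systems". It names as its source the "Braingate2 Clinical Trial in Cleveland that recruits persons with C1-C4 SCI to receive BCI and FES systems".
- **Section 3, item 13** opens by saying that every participant will already have one or two cortical arrays, "as well as stimulating electrodes for restoration of hand and arm function via FES".
- **Section 3, item 12** leaves the boxes for "Device implantation" and "Surgical procedure or Specimen removal during surgery" unticked, so this study implants nothing itself.
- **Section 4, item 21** plans 6 participants, 4 in Cleveland and 2 in Providence.

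**The concern.** Eligibility lists are what site staff apply when they screen. Item 30 covers the brain-interface half of the system twice, once as an inclusion (array and cursor control) and once as an exclusion (poor signals). It does not cover the stimulation half at all. Because the study implants nothing, FES has to be present at entry or it will never be present. A person with an array and no FES could do the virtual-hand tasks in item 13. That person could not do the limb tasks, nor the comparison of the two command sources that item 8 names as a goal, since both sources work by stimulating the person's own muscles.

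The injury wording raises a second question. Item 8 says that people with C5-C7 injury can already regain grasp with EMG-commanded FES, while those with C1-C4 injury have little or no voluntary EMG to use. The level of injury could therefore affect how well the EMG comparator performs. Item 30 sets no level and does not require complete paralysis.

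Providence makes both points more pressing, because item 11's remark about who supplies FES recipients names Cleveland only. At stake would be how many people can inform the FES comparison, and to whom its result applies.

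**Working it through.** There is no figure to reproduce. The protocol gives no power calculation, and item 11 calls the study exploratory. The check is a comparison of texts.

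**Step 1: what item 30 contains.** It has 3 inclusion + 2 exclusion = 5 criteria. Of these, 0 mention FES and 0 give an injury level or require complete paralysis. The omission is as described.

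**Step 2: whether the FES condition is stated elsewhere, and for whom.**

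| Place | What it says on FES | Limited by site? |
|---|---|---|
| Item 9 | The people recruited already have both systems | No |
| Item 11 | The people it aims to enrol (up to four) already have both systems | The number matches Cleveland's 4 in item 20 |
| Item 13 | Every participant already has stimulating electrodes | No |
| Item 38 | Lists risks of connecting to the arm and hand FES electrodes | No |
| Item 44 | Counts connecting and disconnecting the FES system among the study's own risks | No |
| Item 53 | Referral by FES Center staff, from an existing FES study | Consent takes place in the Cleveland VA FES laboratory |

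Items 9 and 13 are enough on their own. Both are unqualified, so they cover the 2 Providence participants as well as the 4 in Cleveland. Item 11's silence on Providence fits its scope of four people and is not evidence that Providence participants lack FES. No item suggests that anyone without FES is expected.

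**Step 3: who applies the criteria.** Under item 31 the principal investigator assesses eligibility in consultation with the co-investigator and the coordinator. Under item 37 the research team discusses each potential participant. Candidates come from a small pool whose implants are known. Enrolling someone without FES by oversight would require these people to overlook the first sentence of their own procedures section.

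**Step 4: the injury descriptions side by side.**

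| Place | Injury described | Status of the text |
|---|---|---|
| Item 8 | Mainly high cervical, with relevance to low cervical | Purpose |
| Item 11 | C1-C4, complete tetraplegia | Enrolment aim |
| Item 24 | High spinal cord injury | Reason for admitting non-Veterans |
| Item 25a | Cervical injury with chronic paralysis | Reason for the target group |
| Item 30 | Any cord injury with some arm paralysis | Entry rule |

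These nest rather than conflict: a person who meets item 11's injury description also meets item 30's injury criterion. An entry rule wider than the intended population is common where candidates are scarce. In Cleveland, membership of BrainGate2 is itself an item 30 criterion, and item 11 says that trial recruits C1-C4 injuries for both systems. This narrows the level in practice for 4 of the 6, though it does not settle completeness.

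**Step 5: effect on the comparison.** In item 13 the same participants attempt the same tasks under both command sources, so a mix of injury levels does not create unequal groups. It could still change the size of the difference from person to person. Item 53 has staff collect each participant's injury history, so results can be described with the injury alongside them.

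**The case for a change.** The strongest reply is that a requirement belongs where screeners look for it. The form's instruction for item 30 asks for criteria detailed enough to define the population, and a prerequisite for a stated aim is an obvious candidate. Item 53 is a privacy answer. Items 26 and 48 describe recruitment and referral through BrainGate without naming FES. For Providence the condition rests on the general wording of items 9 and 13 alone. With so few people, losing even one from the FES comparison would be felt, and one added line costs almost nothing.

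Much of this is right as a matter of drafting. Item 30 is less complete than it could be, and item 53 does not reach Providence. It does not follow that the plan would be carried out differently. The added line would copy what item 13 already says, and it would exclude nobody whom items 9 and 13 allow. A shortfall in the FES comparison arises only if someone is enrolled contrary to those two items, and nothing in the document points to that.

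The injury argument has some substance, since item 8 does link injury level to EMG function. But tightening item 30 to match item 11 has a price. Item 24 calls the candidate population too small to restrict. It says so to justify admitting non-Veterans, but the scarcity is the same. Item 8 also presents the work as relevant to lower injuries.

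**Conclusion.** The textual differences are real, and no change to the plan is needed. The missing FES line is a gap that the rest of the document fills: items 9 and 13 set the condition for all 6 planned participants, and items 38 and 44 assume it. The broader injury wording is a fair trade-off between a target population and a workable entry rule. No sample size, power statement, procedure or analysis would differ if the wording were aligned, so aligning it is an editorial matter.

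This rests on two assumptions. The first is that the investigators treat items 9 and 13 as binding at both sites. If they meant to admit people without FES, for example in Providence, those two items would be wrong and the number available for the FES comparison would need stating; nothing in the document indicates such an intention. The second is that results will be presented with each participant's injury described, which is normal practice in so small a study and possible from the information item 53 collects.

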***Certificate of Confidentiality:**

- Certificates of Confidentiality are issued by the National Institutes of Health (NIH) to protect identifiable research information from forced disclosure.
- They allow the investigator and others who have access to research records to refuse to disclose identifying information on research subjects in any civil, criminal, administrative, legislative, or other proceeding, whether at the federal, state, or local level.
- Certificates of Confidentiality may be granted for studies collecting information that, if disclosed, could have adverse consequences for subjects or damage their financial standing, employability, insurability, or reputation.
- By protecting researchers and institutions from being compelled to disclose information that would identify research subjects, Certificates of Confidentiality help achieve the research objectives and promote participation in studies by assuring confidentiality and privacy to subjects.
- **For more information, see <http://grants1.nih.gov/grants/policy/coc/index.htm>.**

39. Is this project principally concerned with the collection of sensitive information such as sexual attitudes, use of drugs or addictive products, and illegal conduct that would need to be protected against subpoena or forced disclosure in order to protect subjects?

No

Yes- will an application for a *Certificate of Confidentiality be submitted to the National Institute of Health upon IRB approval (or approval contingent on the issuance of such a certificate)?

Yes No provide a justification as to why a Certificate of Confidentiality will not be obtained:

40. Describe all procedures that minimize risks, please include study and standard of care procedures:

Skin irritations - Subjects may experience skin irritation from adhesives or tape. Usually this irritation goes away within an hour. The material in contact with the skin can be changed or moved if the subject's skin becomes extremely irritated.

Electrical safety - All devices used in this study incorporate electrical safety components. Cables that are connected to the subject are electrically isolated from the AC-powered

equipment. The entire experimental setup undergoes electrically safety testing every 6 months, or whenever a new piece of equipment is introduced.

Connecting to the BrainGate2 pedestal connector - A strict protocol is followed when making connections to the pedestals. This procedure involves using sterile gloves, antiseptic wipes, and careful alignment and screwing on of the cable connector.

Privacy breach - Identifiable personal information will be kept on VA computers that are encrypted and password-protected. Printed information will be kept at the VA in a locked file cabinet.

41. Describe alternative procedures or course of treatment, if any, which might be advantageous to the subject. State if no alternatives exist or if this is not a treatment study.

This is not a treatment study.

Minimal Risk: Minimal risk means that the risks of harm anticipated in the proposed research are not greater, considering probability and magnitude, than those ordinarily encountered in daily life or during the performance of routine physical or psychological examinations or tests.

42. Please give your overall risk classification for the research:

- Minimal Risk
 Greater than Minimal Risk

43. Will subjects receive any direct benefit from this research?

- No Yes -describe the direct benefits:

44. Please explain briefly why you consider the risks associated with the study to be reasonable in relation to its benefits?

Although the subjects will not receive any direct benefit from this study, they will assist in determining whether a BCI can be used to control multi-dimensional hand and arm movements, which will help optimize future BCI and FES systems that the subjects may receive. The subjects are already participating in the BrainGate2 research study. The risks that are specific to this study are mostly minimal, involving the additional connecting and disconnecting of the BrainGate2 and FES systems.

Section 6 – Informed Consent

45. Type and number of Consent-

- *When more than one consent form is being used a descriptor MUST be in the header section describing the population and/or phase of the study:*
- Written Informed Consent –number used in this study 1**
- *Oral Script/Letter/Information Sheet- number used in this study *Submit Request for Consent Waiver Form-waiver of documentation of informed consent**
- No informed consent at all in this study- Submit a Request for Consent Waiver Form-waiver of informed consent and proceed to item 53**

46. Will all adult subjects have the capacity to give informed consent?

Yes No- Describe range of impairment.

- Research involving more than minimal risk, capacity should be determined by a psychiatrist, clinical psychologist, or other qualified professional not otherwise involved in the research.
- Individuals who lack the capacity to consent may participate in research only if a legally authorized representative gives consent on their behalf.

47. Will anyone other than the subject be authorized to provide consent or permission for the subject's involvement in the research?

- e.g., parents, court ordered guardian, spouse, etc.

No Yes -please explain: Although the subjects will have the capacity to give informed consent, they may not be physically able to sign the consent form, so a legally authorized representative may sign on their behalf.

48. Describe how and where informed consent will be obtained:

Informed consent will be obtained by the investigator's clinical research staff in consultation with the subject. Generally, the process for obtaining informed consent for participation is as follows: 1) a potential subject is referred to the study by a member of the BrainGate study research team. 2) A member of the research staff explains the study. 3) If the subject believes he/she would like to participate in a project, the informed consent and HIPAA authorization forms are presented and reviewed in detail. This occurs in the VA FES Center laboratory. 4) The investigator and/or research staff answer any questions the subject may have, and the informed consent form is signed and dated. If the subject is physically unable to sign the informed consent form, he/she may instruct their legally authorized representative to sign instead. If the subject is physically unable to sign the HIPAA Authorization form, he/she may instruct their legally authorized representative to sign on the Legal Representative line and print their name on the line below. A witness, unrelated to the study personnel, will observe the Legal Representative's signature and will sign elsewhere on the signature page, and write "Witness" next to their signature. This alternate authorization will be documented in CPRS. If the subject does not have a Health Record, the alternate authorization will be documented in the study research file. A de-identified note describing the alternate authorization will also be sent to the IRB. 5) The subject is given a copy of the informed consent and HIPAA Authorization forms to continue to review at his/her leisure.

The investigators inform all prospective subjects about the purpose and experimental nature of the study, the potential hazards and foreseeable risks involved, and the potential benefits that may result from the study. Subjects are informed that they are free to refuse to participate in the study without prejudicing clinical care; and that if they do participate, they will be free to withdraw at any time without prejudicing clinical care. They are instructed to notify the investigators should they decide to withdraw from the study. Patients are not obligated to reveal their reasons for withdrawal or non-participation to the investigator.

49. Will there be an opportunity for potential subject to take the consent form home to discuss participation and options with family members?

Yes No - please explain:

50. List by role who will be obtaining informed consent from subjects or their legally authorized representatives:

- *ex. study coordinator, co-investigator, research nurse, research assistant, PI*

Informed consent will be obtained by the PI or study coordinator

51. Please describe how informed consent will be obtained from subjects who do not read or understand English;

- *identify any languages likely to be encountered, and attach a copy of a translated and authenticated informed consent document*
- *It is appropriate to indicate that you do not anticipate encountering potential subjects who do not speak English based on the population to be studied*

For subjects who do not read, the research staff will read the consent form to the subject, and the subject will take the consent form home to allow family and friends to review the form with the subject. Non-English speaking subjects will have already been excluded as a requirement of the BrainGate2 study enrollment, since they will need to understand English instructions during the testing sessions.

52. Describe who (by Role ex. PI, Coordinator, etc.) and how it will be determined that subjects and/or legally authorized representative understand the research and their rights.

- *ex. question and answer, repeat back parts of the research, describe a procedure...etc*

The investigator or research staff will ask the subject to describe the procedures involved in the study

Section 7 – Privacy and Confidentiality

Privacy - refers to a person's desire to control the access of others to themselves. For example, persons may not want to be seen entering a place that might stigmatize them, such as a pregnancy counseling center that is clearly identified as such by signs on the front of the building. Privacy concerns people, whereas confidentiality concerns data. The research proposal should outline strategies to protect privacy including how the investigator will access information about potential subjects.

In developing strategies for the protection of subjects' privacy, consideration should be given to:

- Methods used to identify and contact potential subjects
- Settings in which an individual will be interacting with an investigator
- Appropriateness of all personnel present for research activities
- Methods used to obtain information about subjects and the nature of the requested information
- Information that is obtained about individuals other than the "target subjects," and whether such individuals meet the regulatory definition of "human subject" (e.g., a subject provides information about a family member for a survey)
- How to access the minimum amount of information necessary to complete the study

Confidentiality - methods used to ensure that information obtained by researchers about their subjects is not improperly divulged. Confidentiality refers to the researcher's agreement with the subject about how the subject's identifiable private information will be handled, managed, and disseminated. The research proposal should outline strategies to maintain confidentiality of identifiable data, including controls on storage, handling, and sharing of data. When appropriate, certificates of confidentiality could be used to maintain the confidentiality of identifiable data

When the IRB evaluates research proposals for strategies for maintaining confidentiality, where appropriate, consideration will be given as to whether:

- Methods to shield subjects' identity adequately protect subject privacy

- There is a long-range plan for protecting the confidentiality of research data, including a schedule for destruction of identifiers associated with the data
- The consent form and other information presented to potential research subjects adequately and clearly describe confidentiality risks.
- The informed consent process and the informed consent document, and if applicable the Authorization Form, clearly delineates who will have access to the subject's information and under what circumstances data may be shared (i.e., government agencies, sponsors).

53. Describe when and where subjects will provide their information. Include the nature of the information and who will receive and use the information. Document the provisions used to protect privacy interests of those subjects when gathering their information and data.

FES Center staff will refer subjects to the study, since we will be recruiting subjects from an existing FES study. We will only get information about a subject if the subject requests that the referrer forwards their contact information to our research team. We would then schedule an appointment for them to sign the HIPAA authorization form and review the consent form. Potential participants will undergo the consenting process in a private room in the VA FES Center laboratory. After the subject signs the consent form, and while still in a private room in the VA FES Center laboratory, the research staff will collect the necessary personal information, such as contact information (name, address, phone number, email address, emergency contact information), demographics information (date of birth, gender, race) and information about their spinal cord injury (injury history, medical status, and medical complications related to the spinal cord injury). This personal information will only be collected at recruitment. The identifiable private information will be kept by the investigator and research staff at the VA. No identifiable private information will leave the VA. The subject will be assigned a research code, and only that code will be used outside the VA to identify the subject. The research code will be used for all other information collected in the study (neural data, stimulation parameters, results of EMG measurements, videos of any procedures performed as part of this study, and written records of incidents related to the study). Even though only de-identified data will leave the VA, due to the small number of subjects (1 or 2 at a time), it is possible that the study sponsor, the local external IRB, and the local research team outside the VA may be able to identify the data. The privacy requirements of the local external IRB will still limit any further identification of the subject data.

54. Will researchers have access to identifiable private information about potential subjects outside of this research project? *Ex. PI is provider who has access to medical records for clinical care*

No Yes- please explain:

55. Will Researchers collect identifiable private information on anyone other than the subject?

- *Ex. family members, friends, colleagues, classmates...etc.*

No Yes -please explain:

56. At the time data are transcribed or recorded for this study they are?

Fully identifiable- list identifiers to be collected:

Coded with a unique identifier- describe the code: The code will be 2 letters (representing the study) followed by a 1-2 digit number (representing the subject).

a. Who will have access to the key? The study coordinator and the PI.

b. Where is the key maintained? Two locking barriers must be in place between the coded data and the key. The key will be maintained in a locked cabinet in a locked office in the VA FES Center laboratory (Rm. B-E253), and electronically on a VA server.

De-identified-by Privacy Officer or Statistician.

Other (describe):

57. How will electronic research data be secured while the study is active?

No electronic data will be stored

VA encrypted laptop

Encrypted VA device/media- describe:

VA network drive;

M: drive; whose?

S: drive

Folder access password protected

Other drive location (for example P: drive):

Folder access password protected

58. How will hardcopy research data be secured while the study is active? Two locking barriers must be in place.

No hardcopy data will be stored

Locked office and locked file cabinet

Data coded by PI or study staff with a master list secured and kept separately

Data de-identified by Privacy Officer or Statistician- (VA does not consider coded data to be de-identified)

Other -specify:

59. Provide the physical location including room number (and address if outside of this VA) where all electronic and hardcopy data will be stored: Room B-E238 in the VA FES Center laboratories.

60. Is identifiable information physically or electronically sent TO the LSCDVAMC from other institutions or locations?

No Yes - contact Privacy Officer [name] or [name] [contact] / [contact] [contact] / [name] or Information Security Officer [name] [contact] / [contact] – prior to submitting to the Research Service.

